12.2 Adverse Event Recording

Each AE experienced by a patient, either spontaneously revealed by the patient or observed by the Investigator, whether believed by the Investigator to be related or unrelated to the study product, must be recorded on the patient's hospital notes and on the appropriate section of the eCRF.

12.2.1 Events occurring within one hour after injection

The presence and intensity of local and systemic AEs occurring within one hour after injection will be recorded by the study staff according to the intensity scale in World Health Organization (WHO) Toxicity Scale (Appendix 10).

12.2.2 Diary cards

After each study product administration, patients will be provided with a diary card. These will include the definitions of mild, moderate and severe AEs, as described in Section 12.1.2, in order to facilitate the assessments by the patients of their own level of functional impairment for each experienced AE.

The diary card will be used to record from Day 1 to Day 7 after each immunization, with Day 1 being the day of study product administration, the presence or absence and intensity of the following solicited AEs:

- Local AEs, at each injection site:
 - Pain, itching with grading of intensity.
 - Swelling, redness, induration with measurement of size (in millimeters).
- Systemic AEs:
 - Temperature (°C).
 - Nausea, fatigue, myalgia, headache, with grading of intensity.

Patients will also have the possibility to record unsolicited adverse events.

Patients will be instructed to bring their diary card with them to the unit when they return for their visits. Following discussion of symptoms with the Investigator, information on local tolerability/AEs will be recorded in the eCRF, as appropriate. Diary cards will be retained with the patient's source notes after completion.

12.3 Adverse Event and Pregnancy Reporting

12.3.1 Adverse event reporting

Any medical condition that is present at the time that the patient gives informed consent should be considered as pre-existing and not reported as an AE. However, if it deteriorates at any time during the study, it should be recorded as an AE.

All SAEs will also be:

- Recorded on the relevant SAE reporting form and followed up through to resolution by an Investigator,
- Then, submitted to the Pharmacovigilance Department of the contracted CRO,
- Then, submitted by the contracted CRO to Neovacs SA.

Contact Details for SAEs can be found in the “Guidelines for completing SAE and pregnancy forms” document.

All SAEs and FUP of SAEs, regardless of relationship, will be reported via fax or via e-mail ([contact]) by the site within 24 hours of the Investigator becoming aware of the event.

Other supporting documentation of the event may be requested and should be provided as soon as possible.

All SAEs will be followed up until satisfactory resolution or until the Investigator deems the event to be chronic or the patient to be stable.

Following notification by the Investigator, Neovacs SA's delegate for Pharmacovigilance will report events that are both serious and unexpected and are associated with study product(s) to the Regulatory Health Authorities within the required timelines: **fatal and life threatening events within 7 calendar days and all other SAEs within 15 calendar days**, or according to local requirements if appropriate.

The classification of expectedness will be based on the material provided in the current version of the IB.

12.3.2 Pregnancy reporting

Any pregnancy that occurs during the study must be recorded on a pregnancy notification form and reported to the contracted CRO with 24 hours of learning of the occurrence (as described in Section 12.3.1). In case of pregnancy, unblinding procedure must be performed. The pregnancy should be followed up to determine its outcome (i.e., healthy birth, spontaneous or voluntary abortion, presence or absence of any birth defects, congenital abnormality, or maternal and/or newborn complications). A pregnancy report should include the Investigator's assessment of any possible relationship between the outcome and the exposure to study products.

12.4 Emergency Medication

The possibility that IFN-K can cause anaphylaxis in humans cannot be excluded. All participating centers should therefore be equipped to manage cardiovascular resuscitation with adequate material ready for use at the time of study product administration and during the 1 hour observation period after each administration.

Please refer to Section 10.2.2 for emergency unblinding and contact details of Neovacs SA's Clinical Safety Physician and Delegate Medical Monitor.

13. STATISTICAL ANALYSES

An electronic data capture (EDC) system will be utilized for this study. The statistical analysis of these data will be performed by an independent CRO. All data will be listed, and summary tables will be provided.

This section describes the statistical analysis as it is foreseen at the time of planning the study. Any major deviations from this plan, the reasons for such deviations, and all alternative or additional statistical analyses that may be performed will be described in the Statistical Analysis Plan (SAP), which will give a detailed technical description of all statistical analyses.

13.1 Determination of Sample Size

The primary objective of this study is to evaluate the neutralization of the IFN gene signature following treatment with IFN-K, as measured by the change from baseline of the expression of IFN-induced genes **and** to evaluate the efficacy of treatment with IFN-K using the British Isles Lupus Assessment Group (BILAG)-based Composite Lupus Assessment (BICLA) response criteria. The following assumptions were made for the sample size calculation:

- The error probability for a 2-sided t-test should not exceed 5%;
- The power should be 80% or higher;
- The change of the expression of IFN-induced genes in patients treated with IFN-K is assumed to be -22.6% (data from study IFN-K-001, Lauwerys *et al.*, 2013);
- The change of the expression of IFN-induced genes in patients treated with placebo is assumed to be 10% (data from study IFN-K-001, Lauwerys *et al.*, 2013);
- The common standard deviation of the change is 68 (data from study IFN-K-001, Lauwerys *et al.*, 2013).

The assumptions for the change in expression of IFN gene signature and the standard deviation are based on the original data of study IFN-K-001 as presented in Lauwerys *et al.*, 2013.

With 80 evaluable patients per group i.e. a total of 160 evaluable patients, the study will have a power of 85% to detect a difference of 32.6% in the expression of IFN-induced genes in patients treated with IFN-K compared to patients treated with placebo, assuming that the common standard deviation is 68% and using a two group t-test with a 0.050 two-sided significance level.

[figure not shown]
Assuming a rate of 10% drop-out patients, 178 patients should be enrolled in order to have 160 evaluable patients at Week 36 (80 evaluable patients in each treatment arm=90% of the enrolled patients).

Figure 1 shows – as a sensitivity analysis for the sample size calculation - the number of patients requested for analysis for different assumptions for differences in mean values and standard deviation in the sample size calculation. An increase in the difference of mean values of 5% would

decrease the number of required patients by approximately $n=40$, whereas a decrease in mean differences would increase the required sample size by $n=60$. A decrease in the standard deviation of 8 - at the reference point of 30% mean difference – would decrease the sample size by approximately $n=36$, whereas an increase of 8 would increase the required sample size by approximately $n=38$.

Taking into account, that the number of patients will be considerable higher in this trial than in the study IFN-K-001, there is a high probability of a smaller standard deviation that could compensate for a possible smaller difference in mean changes. Therefore the sample size calculation gives a realistic estimate of the patients required for analysis to show a significant difference between active treatment and placebo.

Figure 1: Sample-size for different values of between group differences (expression of IFN-induced genes)

[figure not shown]
Assuming common SD=68 and a 0.05 two-sided type-one error rate

Assuming a BICLA response of 20.6% in the placebo group and 40.6% in IFN-K treated patients (i.e. an absolute difference of 20%) with 80 evaluable patients per group, there will be a 73% power to detect a difference of 20% in the BICLA response criterion.

The sample size needed to ensure a 80% power to the comparison of BICLA response rates between IFN-K and placebo for different response rates in the placebo arm and varying between

groups differences are presented in Figure 2. 97 evaluable patients per group would be needed for a power of 80% to detect a difference of 20% with a placebo response rate of 20.6%.

Figure 2: Sample-size for different values of between group differences (BICLA Response rate)

Assuming a power of 80% and a 0.05 two-sided type-one error rate

13.2 Primary Efficacy Endpoint

Two co-primary endpoints will be evaluated in the trial:

- Change from baseline in the expression of IFN-induced genes at Week 36.
- Response to treatment with IFN-K as measured by the British Isles Lupus Assessment Group (BILAG)-based Composite Lupus Assessment (BICLA) response criteria at Week 36:
 - All BILAG A scores at baseline improve to B/C/D and all BILAG B scores improve to C/D at Week 36
and
 - No BILAG worsening in other body systems: no new BILAG A or ≥ 2 new BILAG B scores at Week 36
and

- No worsening in SLEDAI-2K total score at Week 36 compared with baseline
and
 - No deterioration in PGA (< 10% worsening) on VAS 100 mm at Week 36 compared with baseline
and
 - No addition or increased dose level of anti-malarial drugs or immunosuppressive drugs or corticosteroids between Week 24 and Week 36

13.3 Secondary Endpoints

13.3.1 Clinical Secondary Endpoints

- Response to treatment with IFN-K, as measured by the SLE Responder Index (SRI)-4 response criteria at Week 36:
 - Reduction ≥ 4 points in SELENA-SLEDAI
and
 - No new BILAG A
and
 - No more than 1 new BILAG B
and
 - No deterioration in PGA (< 10% worsening) on VAS 100 mm compared with baseline
- Response to treatment with IFN-K, as measured by SLEDAI response, defined as a reduction of the SLEDAI-2K score of at least 4 points at Week 36 compared to baseline
- Response to treatment with IFN-K, as measured by BILAG grade changes by body system
- Response to treatment with IFN-K, as measured by Incidence of SLE flare (SELENA SLEDAI flare index. BILAG flares)
- Response to treatment with IFN-K, as measured by SLICC/ACR-DI
- Response to treatment with IFN-K, as measured by Cutaneous LE Disease Area and Severity Index (CLASI)

13.3.2 Immunogenicity Secondary Endpoints

At time points specified on the flow chart (Table 1), Geometric Mean Titers (GMT) and seroconversion rates for:

- Anti-IFN α binding antibody titers
- Anti-IFN α neutralizing antibody titers

- Anti-KLH binding antibody titers

13.4 Safety Endpoints

- Occurrence, intensity and relationship of any solicited local and systemic AEs during a 7-day follow-up period (i.e. day of study product administration and 6 subsequent days) after each IFN-K or placebo dose
- Occurrence, intensity and relationship of unsolicited local and systemic AEs occurring throughout the study period
- Occurrence and relationship of all SAEs occurring throughout the study period
- Occurrence and intensity of solicited local reactions 1 hour post study product administration
- Occurrence and intensity of solicited systemic reactions 1 hour post study product administration
- Hematological and biochemical levels within or outside the normal ranges and percent change from baseline at each visit
- Occurrence, intensity and relationship of any abnormality in physical examination, vital signs, 12-lead ECG, clinical laboratory evaluations
- Rate and severity of viral infections

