11.5.4 Laboratory Assays

The tests to be conducted throughout the study are described in Table 6. Collection and shipment procedures are described in the Laboratory Manual.

Table 6 Laboratory Assays

Read Out	Analyses	Laboratory
Hematology/Coagulation	Complete blood cell count and differential (RBC, WBC, Lymphocytes, Neutrophils, Platelets); CD19; Total lymphocytes, CD4+, CD8+	Central Safety Laboratory
	Hemoglobin	
	Prothrombin time (PT)	
	Partial Thromboplastin Time (PTT)	
	Fibrinogen	
Biochemistry	Alanine Aminotransferase (ALT) ¹	Central Safety Laboratory
	Aspartate Aminotransferase (AST) ¹	
	Alkaline phosphatase ¹	
	Creatine phosphokinase (CPK)	
	Creatinine ²	
	Urea	
	Total proteins	
	Albumin	
	Coomb's test (direct)	
	Circulating Anti-Coagulant	
Viral Serology	HBsAg	Central Safety Laboratory
	Antibodies to HCV, HIV, HTLV 1-2	
	IgG to HSV (HSV-1 and HSV-2), VZV, CMV and EBV	
High risk HPV	COBAS HPV test	Central Safety Laboratory
Pregnancy test	Serum β-hCG	Central Safety Laboratory
	Urine β-hCG	Local Laboratory
Urine testing	Dipstick urinalysis (pH, glucose, etc)	Local Laboratory
	Microscopic examination (RBC, WBC, urinary casts)	Central Safety Laboratory
	Albumin, creatinine, protein concentrations	
Binding Antibodies	Anti-IFNα antibodies	Central Specialized Laboratory
	Anti-KLH antibodies	
Neutralizing Antibodies	Anti-IFNα antibodies	Central Specialized Laboratory
Other Antibodies	e.g. IFNβ cross neutralization	Central Specialized Laboratory
Autoantibodies	Antinuclear antibodies (ANA)	Central Safety Laboratory
	Anti-dsDNA antibodies	
	Anti-Sm, anti-RNP antibodies	
	Anti-SSA/Ro antibodies	
	Anti-SSB/La antibodies	
	Anticardiolipin antibodies (IgG, M, A)	
	Anti-β ₂ -glycoprotein I antibodies	
Inflammatory markers	C3, C4, CH50	Central Safety Laboratory
IFN gene signature ³	IFNα-inducible genes	Central Specialized Laboratory

* See Laboratory Manual for more details and for exact volumes of blood and types of samples at each visit

¹ Not required for disease-oriented testing at Visit 5, Visit 7, Visit 8, Visit 10 and Visit 11.

² Creatinine clearance GFR will be calculated using the Cockcroft-Gault formula: CrCl GFR = (140-age) * (Wt in kg) * (0.85 if female) / (72 * Cr) and MDRD formula: GFR = 170 x [serum creatinine (mg/dl)]-0.999 x [age]-0.176 x [serum urea (mg/dl)]-0.17 x [serum albumin (g/dl)]0.318 x [0.762 if female] x [1.180 if African ancestry]

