5.2.4.3 Secondary efficacy analyses

Secondary efficacy analyses will be performed on the FAS population except if otherwise specified.

5.2.4.3.1 *SRI response*

The SRI-4, 6, 8, 10 responses will be described at Week 36. (Statistical tables 14.2.5.1, 14.2.5.4, 14.2.6.1, 14.2.7.1, 14.2.8.1)

The SRI-4 response (section 4.1.2.1) will be analyzed using the same method as the primary analysis for the second co-primary endpoint (logistic regression). This analysis will be performed both on the FAS and PP sets. (Statistical tables 14.2.5.2 & 14.2.5.5)

The model on FAS for patients IFN-K treated with the status of IFN α neutralizing antibodies (positive/negative) at Week 36 as dependent variable will be also presented (Statistical table 14.2.5.3).

The SRI-6, 8, 10 responses to treatment at week 36 will also be analyzed using a logistic regression using the response rate as dependent variable and treatment as independent variable, while adjusting for the minimization factors used for randomization. (Statistical tables 14.2.6.2, 14.2.7.2, 14.2.8.2)

All analyses performed on SRI-4 will also be conducted on the composite SRI-4 (both with tapering CS \leq 5 mg and \leq 7.5 mg) on the FAS population only. (Statistical tables 14.2.5.6 to 14.2.5.11)

The SRI-4 response is an important and alternative endpoint assessing the clinical response. In case, there will be no trend on the BICLA response, the SRI-4 response could be chosen as primary endpoint for further development of IFN-K.

5.2.4.3.2 *SLEDAI response*

Number of patients achieving a SLEDAI response, defined as a reduction of the SLEDAI-2K score of at least 4 points at Week 36 compared to baseline will be analyzed using frequency table methods (Statistical table 14.2.9).

SLEDAI-2K score at each visit and change from baseline by treatment group will also be presented (Statistical tables 14.2.10.1 to 14.2.10.2).

All SLEDAI data will be listed in Listing 16.2.6.2.

5.2.4.3.3 *BILAG*

Shift tables between Baseline and LVA (last available value between Week 36 and Week 24) will also be presented for each body system. (Statistical table 14.2.11)

Finally, descriptive statistics for the BILAG global score at each visit and change from baseline to LVA will be presented. The difference between treatment groups for the change from baseline to LVA will be analyzed using the non-parametric Wilcoxon-test. (Statistical table 14.2.12)

Statistical Analysis Plan

Study Name: IFN-K-002

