5.2.5.3 Laboratory safety variables

Laboratory evaluations will be summarized by visit and by treatment group on the Safety population.

For each hematology, chemistry and coagulation variables:

- Quantitative descriptive statistics will be tabulated at each visit over the course of the study for raw values and change from baseline (Statistical tables 14.3.15.1, 14.3.15.2, 14.3.16.1, 14.3.16.2, 14.3.17.1, 14.3.17.2.)
- Qualitative descriptive statistics will be tabulated for each laboratory variable at each time over the course of the study:
 - By clinical significance (normal, Abnormal CS/N, Abnormal CS/AE, Abnormal NCS) (Statistical tables 14.3.15.3, 14.3.16.3, 14.3.17.3)
 - by grade (if applicable) (Statistical tables 14.3.15.4, 14.3.16.4, 14.3.17.4)

All urinalysis parameters will also be analyzed as quantitative variables (Statistical table 14.3.18)

In addition, the incidence of severe infections based on the total T-lymphocyte count (lymphocytes < 1000 versus lymphocytes > 1000/mm³) at the visit 2 (D0) will be presented (Statistical table 14.3.19).

Statistical Analysis Plan

Study Name: IFN-K-002

SAP version & date: v4, 18/Jun/2018

All laboratory results will also be presented in Listings 16.2.8.1 to 16.2.8.3.

Urine analysis data will be listed in Listing 16.2.8.4.

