5.4.4 Retest and Unscheduled visits

During the data review meeting, any data from unscheduled visit which must be taken into account in the analysis will be identified.

Other data from unscheduled visits will only be tabulated in listings.

6 Interim analysis

No interim analysis is planned.

7 Modifications from the statistical sections in the protocol

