14.3.12.4	SAEs by SOC, PT and relationship - Period [3rd dose; 4th dose[X			
14.3.12.5	SAEs by SOC, PT and relationship - Period [4th dose; 5th dose[X			
14.3.12.6	SAEs by SOC, PT and relationship - Period [5th dose; Week 36]		X			
14.3.12.7	SAEs by SOC, PT and relationship - Period [Last dose; Week 36/Early Termination]		X			
14.3.13.1	SAEs by SOC, PT and intensity - Before 1st dose		X			
14.3.13.2	SAEs by SOC, PT and intensity - Period [1st dose; 2nd dose[X			
14.3.13.3	SAEs by SOC, PT and intensity - Period [2nd dose; 3rd dose[X			
14.3.13.4	SAEs by SOC, PT and intensity - Period [3rd dose; 4th dose[X			
14.3.13.5	SAEs by SOC, PT and intensity - Period [4th dose; 5th dose[X			
14.3.13.6	SAEs by SOC, PT and intensity - Period [5th dose; Week 36]		X			
14.3.13.7	SAEs by SOC, PT and intensity - Period [Last dose; Week 36/Early Termination]		X			
14.3.14	SAEs leading to permanent study drug discontinuation by SOC and PT		X			
14.3.15.1	Hematology - Value at each visit		X			
14.3.15.2	Hematology - Change from baseline		X			
14.3.15.3	Hematology - Abnormalities at each visit		X			
14.3.15.4	Hematology - Grade at each visit		X			
14.3.16.1	Chemistry - Value at each visit		X			
14.3.16.2	Chemistry - Change from baseline		X			
14.3.16.3	Chemistry - Abnormalities at each visit		X			
14.3.16.4	Chemistry - Grade at each visit		X			
14.3.17.1	Coagulation - Value at each visit		X			
14.3.17.2	Coagulation - Change from baseline		X			
14.3.17.3	Coagulation - Abnormalities at each visit		X			

Statistical Analysis Plan

Study Name: IFN-K-002

SAP version & date: v4, 18/Jun/2018

Number	Title	Screened	SAF	FAS	PP	Other
14.3.17.4	Coagulation - Grade at each visit		X			
14.3.18	Urinalysis - Value at each visit		X			
14.3.19	Incidence of severe infections at D0		X			
14.3.20.1	Weight and BMI - Value at each visit		X			
14.3.20.2	Weight and BMI - Change from baseline		X			
14.3.21	Physical examination, Body system at each visit		X			
14.3.22.1	Vital signs - Value at each visit		X			
14.3.22.2	Vital signs - Change from baseline		X			
14.3.23	ECG - Abnormalities at each visit		X			
14.3.24	Concomitant medications		X			

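### The laboratory tables show toxicity grade only visit by visit, so no table counts patients, by arm, whose grade became new or worse after the first dose

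*Protocol*

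**What the plan says.** Two bullets of Protocol 13.4 matter. One asks for "Hematological and biochemical levels within or outside the normal ranges and percent change from baseline at each visit". Another asks for the occurrence, intensity and relationship of any abnormality in the clinical laboratory evaluations, among other assessments.

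SAP 5.2.5.3 plans for haematology, chemistry and coagulation:

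- "Quantitative descriptive statistics will be tabulated at each visit over the course of the study for raw values and change from baseline". SAP 7.4 drops percent change in favour of absolute change, although SAP 4.2.2 still names percent change.
- "Qualitative descriptive statistics will be tabulated for each laboratory variable at each time over the course of the study", once by clinical significance and once by grade.

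SAP 10.1 turns this into four tables per panel, 14.3.15.1 to 14.3.17.4. "Hematology - Grade at each visit" is typical. Baseline abnormalities are in separate tables (14.1.13 to 14.1.15).

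The only shift table in the SAP is for efficacy, in 5.2.4.3: "Shift tables between Baseline and LVA (last available value between Week 36 and Week 24) will also be presented for each body system".

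On unscheduled visits, SAP 5.4.4 says that at the data review meeting "any data from unscheduled visit which must be taken into account in the analysis will be identified", and then: "Other data from unscheduled visits will only be tabulated in listings". It gives no criterion for the selection.

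**The concern.** Whether an abnormality occurred, and how severe it became, is a question about each patient over the treatment period. A by-visit prevalence answers another question: how many patients with a value are abnormal on that day. It does not show whether the abnormal patients at Week 8 are those at Week 12, or whether they were already abnormal at entry.

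Baseline abnormality is expected here. Leukopenia, lymphopenia and thrombocytopenia are among the classification criteria in Appendix 1, and low white cells and platelets score in SLEDAI-2K (Appendix 2). Exclusion criterion 10 in Protocol 8.3.2 does not reach SLE-related abnormalities.

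Denominators also move: SAP 5.1.1 uses available values, so patients who leave drop out of later visits' percentages.

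Only 21 patients received IFN-K in the earlier study (Protocol 5.4.3), and Protocol 5.5 gives confirming the preliminary safety information as a reason for this trial before a larger one. At stake is a plain count by arm of patients with an emergent cytopenia or liver enzyme rise.

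**Working it through.** **Tables.** Three panels with four tables each make 12. Counts that cross baseline with later grade, take the worst later grade, or count patients with a new or worse grade: 0 of 12.

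**Visits.** Protocol Table 1 and 10.9 give the complete panel at Visits 4, 6, 9 and 12 and the disease-oriented panel at Visits 5, 7, 8, 10 and 11, so 4 + 5 = 9 post-baseline visits. For ALT, AST and alkaline phosphatase, the footnote in Protocol 11.5.4 says "Not required for disease-oriented testing at Visit 5, Visit 7, Visit 8, Visit 10 and Visit 11", which leaves 4.

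**Why the count cannot be rebuilt.** Suppose each of nine grade tables shows 2 patients at grade 3 in one arm. The number of different patients lies anywhere from 2 (the same two throughout) to 2 × 9 = 18. With four visits it is 2 to 8. If the baseline table also shows 2 at that grade, the emergent count could be as low as 0.

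**Size, under assumptions.** The documents give no laboratory event rates, so all rates below are assumed. The only planned figure used is 89 per arm (160/0.90 = 177.8, so 178, half in each arm). Let *b* be the proportion already at the grade of interest and staying there, *c* the proportion of the others who worsen (4% placebo, 12% IFN-K), *d* the number of visits an event lasts, and *k* the number of visits, with events spread evenly.

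- Emergent incidence: (1 − *b*) × *c*
- By-visit prevalence: *b* + (1 − *b*) × *c* × *d*/*k*

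For *b* = 15%, emergent incidence is 0.85 × 4% = 3.4% against 0.85 × 12% = 10.2%, about 3 against 9 of 89 patients. With *k* = 9 and *d* = 1, prevalence is 15% + 3.4%/9 = 15.4% against 15% + 10.2%/9 = 16.1%.

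Between-arm difference in percentage points:

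| *b* | Emergent count | By visit, *k* = 9, *d* = 1 | By visit, *k* = 9, *d* = 3 | By visit, persistent | By visit, *k* = 4, *d* = 1 |
|---|---|---|---|---|---|
| 0% | 8.0 | 0.9 | 2.7 | 8.0 | 2.0 |
| 15% | 6.8 | 0.8 | 2.3 | 6.8 | 1.7 |
| 30% | 5.6 | 0.6 | 1.9 | 5.6 | 1.4 |

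Persistent means present at every post-baseline visit. The difference in points is then the same as for the emergent count, but it sits on top of the baseline cases: for *b* = 15%, 18.4% against 25.2%.

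**Power as a yardstick only** (two proportions, normal approximation, two-sided 5%, 89 per arm). For *b* = 15%, the emergent count has 44%. One by-visit table has about 5% for one-visit events and about 20% for persistent ones. For *b* = 0%, the emergent count has 50%, against about 10% and 50%.

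**The case against.** A reader might infer that emergent toxicity is invisible throughout the planned output. The documents do not support that.

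- Protocol 12.1.2 makes a clinically significant abnormality that is not normal for the study population (CS/AE) an adverse event. It then enters the patient-level TEAE summary (14.3.2) and the tables by relationship and intensity. Those also supply relationship, which a grade table cannot.
- Lupus-typical abnormalities (CS/N) are tabulated apart from CS/AE ones.
- Change-from-baseline tables carry minimum and maximum (SAP 5.1.1), so an extreme at a scheduled visit is seen.
- Grade tables separate the grades, so a stable grade 1 does not conceal a new grade 3.
- Individual results are in Listings 16.2.8.1 to 16.2.8.3, and an independent board reviews safety data (SAP 5.3.3).

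All of this stands, and it limits the point without closing the gap. The CS/AE route rests on investigator judgement, a worsening rated CS/N does not reach the TEAE tables, and the SOC and PT tables are mostly split by dosing period. A minimum or maximum shows one value, not how many patients worsened. Listings and board review give no planned count by arm.

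Two other readings go too far. Nine visits do not apply to liver enzymes. Nor are unscheduled results barred from the analysis: the meeting may bring them in, and the gap is that no criterion is stated. The sharpest contrast also assumes that each event lasts a single visit. The laboratory analysis is descriptive, so no planned test loses power.

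**Conclusion.** The point holds as an incomplete summary of a named safety endpoint; it does not invalidate a conclusion. The by-visit tables match the bullet that itself asks for results at each visit. The bullet on occurrence and intensity is only partly answered, because no table gives a per-patient count by arm of new or worsened grades and none can be derived from those planned.

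The size depends on event duration. Under the assumed rates, with 15% abnormal at baseline, the by-visit difference for one-visit events is 0.8 point over nine visits or 1.7 points over four, against 6.8 points emergent. For persistent events the difference is the same 6.8 points on a higher base. The missing link to baseline and the impossibility of rebuilding the count need none of these assumptions. The change is worth making because it is cheap.

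**What to change.** In SAP 5.2.5.3 add, for each graded haematology, chemistry and coagulation parameter, in the safety population by arm:

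- a table of baseline grade against worst post-baseline grade up to Week 36, using scheduled and unscheduled results;
- n (%) with an increase of at least one grade;
- n (%) with a new grade 3 or 4.

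The denominator is patients with a baseline value and at least one later value. Add the tables to SAP 10.1, and amend SAP 5.4.4 so that unscheduled laboratory results enter them by rule. Keep the by-visit tables.

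The cost is a few more tables from data already collected and graded. No procedure, endpoint or test level changes. The one drawback is that patients with more retests have more chances of a high worst grade, so a footnote giving the number of unscheduled results by arm would help.
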